Medically-Tailored Meals to Prevent Recurrent Hepatic Encephalopathy: The BRAINFOOD Pilot Trial

Date of IRB Approval: January 4, 2021

NCT04675775

Medically-Tailored Meals to Prevent Recurrent Hepatic Encephalopathy: The BRAINFOOD Pilot Trial

Principal Investigator (PI):

[name]

Division of Gastroenterology and Hepatology
Department of Internal Medicine
University of Michigan, Ann Arbor, MI

Correspondence:

[name]
[name]
[name]
P: [contact]
F: [contact]
e: [contact]

Key words: Cirrhosis, Ascites, Liver Disease, Nutrition, Frailty, Sarcopenia

Disclosures: No conflicts of interest to disclose

SUMMARY

Study Name	Medically-Tailored Meals to Prevent Recurrent Hepatic Encephalopathy: The BRAINFOOD Pilot trial
Subject Population	Stage 1: At least 30 patients with cirrhosis including 10 with compensated cirrhosis, 10 with moderate to severe ascites and 10 with a history of overt hepatic encephalopathy (HE) Stage 2: At least 20 patients with cirrhosis and a recent history of overt HE
Objective	To determine the feasibility of a trial that uses medically-tailored meals (MTM) as an intervention in persons with a history of HE
Design	Two-stage feasibility trial
Stages	Stage 1: Feasibility of assessments Stage 2: Pre-Post trial after refining selection of assessments based on patient ability to complete and detect changes
Procedures	
 - Stage 1 & Stage 2: Screen for patients with cirrhosis and recent episode of overt HE and/or ascites. - Consent eligible patients. - Stage 1: Feasibility of assessments 
 • Complete baseline assessments in-person • Subjects receive a nutrition education hand-out and 2 weeks of MTM. They undergo 24-hour dietary recalls during this intervention phase. • Subjects complete final study visit at 4\pm1 weeks in-person and complete all assessments - Stage 2: Pre-Post trial after refining selection of assessments based on patient ability to complete and detect changes from Stage 1. 
 • After enrollment, there is a 4\pm1 run-in phase to demonstrate interest • Subjects return for in-person visit to complete baseline assessments • Subjects receive a nutrition education hand-out and 6 weeks of MTM. They undergo 24-hour dietary recalls during this intervention phase. • Subjects return for in person visit at 11\pm2 weeks and complete all assessments. There is a 12-week observational period. • Subjects complete final study visit at 24\pm3 weeks via phone.
Primary Outcomes	
 1. Overall subject retention rate, defined as subjects who complete all study visits (Stage 1 & Stage 2). 2. Subject adherence rate to MTM intervention (Stage 2 only).
Secondary Outcomes	
 1. Proportion of subjects who complete all study assessments and procedures. 2. The time required to complete assessments (Stage 1 only). 3. The number of eligible candidates screened and proportion of those enrolled. 4. Subject drop-out rate.
Exploratory Outcomes	
 1. Determine if MTM improves the subject's nutritional intake (Stage 2 only). 2. Determine if MTM affects the subject's cognitive function or health-related quality of life (HRQOL) (Stage 2 only). 3. Explore whether MTM affects clinical outcomes and healthcare utilization rates (Stage 2 only). 4. Patient satisfaction and preferences of MTM (Stage 2 only).

Table of Contents

SIGNIFICANCE	5
1. STUDY OBJECTIVES	6
1.1 Specific Aims	6
1.1.1 Primary Aims	6
1.1.2 Secondary Aims	6
1.2 Exploratory Outcomes	7
1.3 End Points	8
2. STUDY DESIGN	8
3. SELECTION AND ENROLLMENT OF SUBJECTS	9
3.1 Inclusion Criteria	9
3.2 Exclusion Criteria.....	11
3.3 Study Enrollment Procedures	11
3.3.1 Identification & Recruitment.....	11

HE is caused by brain exposure to ammonia, a waste product of bacterial metabolism in the gut. Normally the liver converts ammonia to urea. In cirrhosis, however, ammonia is distributed peripherally. Muscle is the main auxiliary site of ammonia clearance. Ammonia detoxification by muscle consumes branched-chain amino acids that are liberated in a catabolic process.(15) A vicious cycle emerges. **Hyperammonemia begets sarcopenia which, in turn, raises blood ammonia levels.**(16) Sarcopenia is present in \geq 50% of patients with cirrhosis.(8) Contrary to the widely held myth that excess protein intake raises ammonia levels and HE risk, increased protein intake is safe in patients with cirrhosis including those with history of HE.(17) To reduce recurrent HE, patients are recommended to consume a high protein diet.(18)

Nutrition is a central component in management of cirrhosis complications. Guidelines recommend that patients with HE receive a high protein diet with 1.25 g/kg ideal body weight (roughly 1 g/kg actual body weight).(18) Protein supplementation has been shown to improve health related quality of life (HRQOL) and to reduce the risk of HE.(19, 20) Unfortunately, implementation of a high-protein diet is challenging. Food insecurity and poverty are highly prevalent among patients with cirrhosis.(21) Furthermore, most patients with cirrhosis, particularly those with ascites, report severe anorexia.(22)

One solution to the problem of malnutrition and therefore recurrent HE is to provide standardized meals for the short-term during the high-risk period after an HE episode. Medically-tailored meals (MTM) have been linked to reductions in expected readmissions and the incidence of falls for nutritionally at-risk elders.(23, 24) Low-sodium MTMs have been shown to be cost-effective and to improve quality of life in patients with hypertension.(25) In a recent randomized controlled trial, patients with acutely decompensated congestive heart failure were randomized to receive home-delivered low-salt meals or usual care.(26) This study demonstrated a substantial reduction in the risk of readmission.(27) We recently completed a 1:1 randomized trial of high-protein, low-sodium home-delivered meals versus standard of care (diet education) for 40 patients with refractory ascites (aged 60 on average).(NCT03493204) The meals improved need for paracentesis, quality of life, and physical function at a cost of \$500/person-month. We now turn our attention to the prevention of HE. The BRAINFOOD study proposes to determine whether home-delivered high protein MTM can reduce recurrent HE in patients with a recent episode of overt HE. Before proceeding with a large-scale trial, we will conduct a pilot feasibility trial.

1. STUDY OBJECTIVES

The primary objective is to determine the feasibility of conducting a future definitive randomized-controlled trial of MTM in a study population with a history of overt HE. This feasibility trial will be conducted in two stages. Stage 1 will evaluate the feasibility of all assessment processes among three different populations of cirrhosis patients. The results of Stage 1 will be utilized to improve study processes and procedures of Stage 2 prior to the start of Stage 2 enrollment. Stage 2 will evaluate MTM intervention fidelity and adherence, determine recruitment and retention rates and determine efficacy of MTM among a pool of cirrhosis subjects with overt HE.

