1.1.3 Exploratory Aims

The exploratory aims of this trial include measuring clinical changes for possible inclusion in the future trial.

- 1) To determine if MTM in Stage 2 improves the subject's nutritional intake by measuring the proportion of subjects who meet protein intake goals (1g/kg/day) and caloric intake goals (30c/kg/day) as assessed using the 24-Hour Diet Recall and/or VioScreen FFQ from baseline to 9 weeks.
- 2) To determine whether MTM in Stage 2 improves reported cognitive function.
 - Comparison of Encephalapp Stroop scores from baseline to 11±2 weeks. We aim to evaluate whether there is normalization in individual scores, by comparing the proportion of subjects with a 'normal' score at baseline to 11±2 weeks, with a score of < 190 seconds defined as normal.
 - Comparison of Animal Naming Test (ANT) scores from baseline to 11±2 weeks and 24±3 weeks. We aim to evaluate whether there is normalization in scores, by comparing the proportion of subjects with a 'normal' score at baseline to 11±2 weeks and 24±3 weeks, with a score of >10 animals defined as normal.
- 3) To determine if MTM in Stage 2 improves self-reported HRQOL.
 - Comparison of Short Form-8 Health Survey (SF-8) score from baseline to 11±2 weeks and 24±3 weeks. We aim to determine the proportion of subjects who experience $\geq 5\%$ improvement in SF-8 score from baseline to 11±2 weeks and 24±3 weeks.
- 4) We will explore patient satisfaction and preferences of MTM with a qualitative assessment conducted at the final study visit conducted via phone at 24±3 weeks.
- 5) We will explore if MTM in Stage 2 improves health outcomes and healthcare utilization rates including:
 - Healthcare Utilization: We will compare number of reported total hospital days, number of Emergency Room (ER) visits, number of paracenteses, number of all-cause hospitalizations, number of hospitalizations due to overt HE and number of subjects who undergo liver transplantation or die at different time points throughout the study, ranging from 90 days prior to enrollment to 24±3 weeks.
 - Clinical Outcomes: Comparison of MELD-Na score, serum albumin concentration, diuretic dose, weight, and HE therapies at different time points throughout the study, ranging from 90 days prior to enrollment to 24±3 weeks.

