2. STUDY DESIGN

Overview: We propose a two-stage trial to determine the feasibility of MTM intervention in cirrhosis patients with a history of HE. Stage 1 will assess the feasibility of 10 different assessments and 2 weeks of MTM among three different cirrhosis populations, 1) patients with a history of \geq Grade 2 HE, 2) patients with a history of moderate to severe ascites and 3) patients with compensated cirrhosis to determine if any of the feasibility concerns are specific to particular cirrhosis complications. Patients from each group will be enrolled in equal proportion with a total of at least 30 subjects. Baseline assessments will be conducted in person at baseline and at the final study visit after completion of 2 weeks MTM intervention at 4 ± 1 weeks.

Figure 1. Stage 1 Study Design

Stage 2 is a pre-post trial after refining selection of assessments based on subject ability to complete procedures and detect changes in outcomes of Stage 1. We will enroll at least 20 subjects with a history of \geq Grade 2 HE. This stage begins with a 4 ± 1 week run-in phase with patients enrolled in person or via phone. Patients are observed in this run-in period to demonstrate interest in completing the study. Subjects will return to the clinic for a study visit in order to complete baseline assessments. Subjects in Stage 2 subjects will receive 6 weeks of MTM. During the intervention phase, subjects will receive weekly phone calls and will also be required to complete dietary recall assessments in order to measure whether they are consuming the MTM. After completion of MTM intervention, subjects will return to the clinic for an in person visit where they will repeat all baseline assessments. Thereafter, there is a 12-week observational period. Subjects will complete their final study visit and exit interview via phone between Weeks 21 and 27; Study Days 150 – 194 (SD 172 \pm 22) in order to complete final assessments.

Figure 2. Stage 2 Study Design

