 - iii. *Severe: Large volume of fluid present in imaging, marked abdominal distention found on exam, and/or patient required recent paracentesis.*
5. ***Group 3:*** *Patients with compensated cirrhosis based on review of clinical documentation verifying that the patient does not have any history or current evidence of decompensation (e.g. HE, ascites, variceal hemorrhage), but was diagnosed with cirrhosis by the criteria listed above.*

Stage 2: We will only enroll subjects with history of HE. All subjects in Stage 2 must meet the following criteria:

1. *Adult ≥ 18 years of age*
2. *Diagnosis of cirrhosis will be based upon:*
 - a. *liver biopsy, OR*
 - b. *history of cirrhosis complication: ascites, variceal bleeding, hepatic encephalopathy, OR*
 - c. *2 of the following 4 criteria:*
 1. *US, CT or MRI imaging findings of cirrhosis (cirrhotic appearing liver, splenomegaly, varices, ascites)*

2. Fibroscan liver stiffness score >13 kPa
3. Laboratory testing: AST/platelet ratio index (APRI) >2.0
4. CT, MRI or EGD showing presence of esophageal varices
3. Patients with history of \geq grade 2 HE within 180 days of enrollment based on review of clinical documentation verifying the event. If a description of HE symptoms is provided in clinical documentation, but it is unclear if it meets Grade 2 criteria, the PI will assess the clinical documentation and provide an HE grade.
 - HE is a clinical diagnosis that is defined by the following grades below. The operational definition of prior HE is an episode of gross disorientation and alterations in consciousness (lethargy to coma) that is reversible with medical therapy (lactulose and hydration):
 1. Grade 1: Changes in behavior with minimal change in level of consciousness
 2. Grade 2: Asterixis or gross disorientation, drowsiness, inappropriate behavior, euphoria
 3. Grade 3: Marked confusion, incoherent speech, sleeping most of the time but arousable to vocal stimuli
 4. Grade 4: Comatose, unresponsive to pain; decorticate or decerebrate posturing

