4.3.2 Intervention

After baseline assessments are complete, the following steps to implement the MTM intervention with subjects will occur in clinic:

1. All subjects will receive Standard of Care (SOC), which is a standardized nutrition education handout containing instructions on following a high-protein+sodium restricted diet (depending on the presence of ascites).
2. All subjects will enroll in MTM designed and prepared by PurFoods, LLC (Des Moines, IA). PurFoods specializes in providing home-delivered, specialized dietitian-curated meals to patients with various medical conditions such as liver disease, chronic kidney disease, cancer and cardiovascular disease. Additional information about the company and their services can be found here: <https://www.momsmeals.com/>. Subjects will receive meals that adhere to their specified nutritional targets dependent upon their cirrhosis complication of hepatic encephalopathy and/or ascites. Subjects with HE will

receive high-protein (approx. 1g/kg/day) and high-calorie (approx. 30c/kg/day) meals. Subjects with HE and ascites will receive high-protein and high-calorie meals that are also low-sodium (<2000g/day). The study coordinator will place an order with PurFoods for each subject after their baseline assessments are complete. Subjects will select from an available menu of meal options each week that adhere to the specified nutritional targets as above. A staff member from PurFoods will contact the subject via phone or email to complete meal selection. Study food will be pre-packaged for storage with preparation (typically microwave heating) to be completed at home by the subject and will be delivered every 1 to 2 weeks under the direction of PurFoods.

3. In addition to home-delivered meals, the study coordinator will provide each subject with a daytime and nighttime protein supplement (approx. 15g protein) to be consumed daily at home during the same study days as MTM. The daytime protein supplement is a protein bar (ZonePerfect or Perfect Bar). The protein supplements will be provided to subjects in person after baseline completion or the study coordinator will ship them to the subject's home if in remote operations.

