6. STATISTICAL CONSIDERATIONS

6.1 SAMPLE SIZE AND ACCRUAL

The sample size for this feasibility study not driven by any hypothesis test but reflects clinical judgement. For stage 1, our prior experience suggests that 10 patients per condition is enough to detect major study barriers. For stage 2, we hope but have no way of knowing whether the intervention will impact the outcomes given its novelty. It is for that reason that we are conducting a pilot with a reasonable number of patients where outliers would not drive results.

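### Stage 2 cannot determine efficacy, and its exploratory 90-day utilization look-back lies inside the 180-day HE eligibility window

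*Combined protocol and SAP*

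**What the plan says.** Section 1 of the combined protocol and SAP makes feasibility of a future randomized trial the primary objective. It then lists tasks for Stage 2, one of which is to "determine efficacy of MTM among a pool of cirrhosis subjects with overt HE".

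The design sections describe something more modest:

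- Section 2: "Stage 2 is a pre-post trial after refining selection of assessments".
- Section 4.3.2: "All subjects will enroll in MTM designed and prepared by PurFoods, LLC". There is no untreated group.
- Section 6.1: "The sample size for this feasibility study not driven by any hypothesis test". The same section admits that the team cannot know whether the intervention will affect outcomes.

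On utilization, exploratory aim 5 in Section 1.1.3 states: "We will explore if MTM in Stage 2 improves health outcomes and healthcare utilization rates". It names hospital days, ER visits, paracenteses, all-cause hospitalizations and HE hospitalizations, to be compared "at different time points throughout the study, ranging from 90 days prior to enrollment to 24±3 weeks". It does not say which periods are set against each other, or whether on counts or rates. Sections 1.2 and 4.3.3 list utilization as a Stage 2 secondary endpoint, but only after enrollment.

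Stage 2 eligibility in Section 3.1 requires at least "grade 2 HE within 180 days of enrollment based on review of clinical documentation verifying the event". The Significance section presents the meals as help "during the high-risk period after an HE episode". By Table 2, meals start about Day 32, after a run-in of about four weeks, and end about Day 74; the final contact is about Day 172.

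**The concern.** A single treated group with no concurrent control shows change, not the effect of the meals. That holds for every before/after comparison in Section 1.1.3: nutrition, Stroop, ANT, SF-8 and utilization.

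Utilization has an extra defect. The 90-day look-back and the 180-day eligibility window both end at enrollment, so the first lies entirely inside the second. Subjects are selected for having had an HE episode in the earlier period, and nothing comparable is required of the later one. HE events per day can therefore fall with no effect of MTM. If raw counts are compared instead, the longer follow-up can make them rise. Either movement could be taken as benefit or harm. Section 1.1.3 says that these measures are being considered for the future trial, so a misreading could carry forward into its planning.

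**Working it through.** The plan gives no power, effect size or event rate, so there is no figure to reproduce.

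**Inputs from the documents.** Eligibility window 180 days (Section 3.1). Look-back 90 days (Section 1.1.3). Final contact Day 172, range 150 to 194 (Section 4.3.3). At least 20 subjects (Section 2).

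**Assumed.** L, the mean number of HE episodes per 180 days, is taken as 0.5 to 4.

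**1. Constant rate, no effect.** Episodes follow a Poisson process, and subjects are selected for at least one in the 180 days before enrollment.

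- Expected episodes in the 90-day look-back: (L/2)/(1 - exp(-L)). This average includes eligible subjects whose episode came before the look-back.
- Expected episodes in any 90 days after enrollment: L/2.
- Expected fall per day: 1 - (1 - exp(-L)) = exp(-L).

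**2. Variation between patients.** With gamma-distributed rates of shape k, the fall is (1 + L/k)^-(k+1). For k = 1 this is 1/(1+L)^2.

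**3. Raw counts.** Expected episodes over 172 days after enrollment: 172L/180.

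| L | 90 days before | 90 days after | Fall per day | Fall, k = 1 | 172 days after |
|---|---|---|---|---|---|
| 0.5 | 0.635 | 0.25 | 61% | 44% | 0.478 |
| 1 | 0.791 | 0.50 | 37% | 25% | 0.956 |
| 2 | 1.157 | 1.00 | 14% | 11% | 1.911 |
| 3 | 1.579 | 1.50 | 5% | 6% | 2.867 |
| 4 | 2.037 | 2.00 | 2% | 4% | 3.822 |

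Variation between patients reduces the fall at the lower rates. The raw counts are equal when 1 - exp(-L) = 90/172, so L = -ln(1 - 90/172) = 0.74. With follow-up of 150 or 194 days the crossing is at 0.92 or 0.62. Above it, raw counts rise with no effect.

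**4. All-cause admissions.** These carry the artefact only through their HE share. Assume that half of HE episodes are admitted and that there are 0.5 other admissions per 180 days. The fall is 1 - [0.5(L/2) + 0.25]/[0.5(L/2)/(1 - exp(-L)) + 0.25] = 34%, 23% and 9% at L = 0.5, 1 and 2.

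**5. Risk raised after an episode.** As a simple check, let the first episode be uniform over the 180 days, with recurrence at r per day afterwards. The look-back rate is [0.5(90r) + 0.5(1 + 45r)]/90 = 0.75r + 0.00556 per day; the later rate is r. The fall is 46% at r = 0.005, 23% at 0.01 and 3% at 0.02. It is zero at r = 0.0222 (2 per 90 days). At r = 0.03 there is a rise of 7%.

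**6. Removing the qualifying episode (constant rate, no effect).**

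- Latest removed: look-back count [L/2 - (1 - exp(-L/2))]/(1 - exp(-L)) = 0.073, 0.169 and 0.425 at L = 0.5, 1 and 2. Against 0.25, 0.50 and 1.00 after, the apparent rise is 3.42-, 2.97- and 2.35-fold.
- Earliest in the 180 days removed: apparent rise 1.27-, 1.21- and 1.13-fold.

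Neither version is free of bias.

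**The case against.** The strongest reply is that the document limits itself repeatedly. The main objective is feasibility, a definitive randomized trial is reserved for later, aim 5 is labelled exploratory, and Section 6.1 disclaims any hypothesis test. This stands, and it keeps the severity low. It does not remove the efficacy clause, which contradicts its own section.

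Second, the contrast of 90 days before with 172 days after is a construction. Section 1.1.3 speaks only of different time points. This also stands: the calculation shows what one natural reading would give. Time after enrollment also includes a run-in without meals. Under the constant-rate model the run-in is an untreated period outside the selection window. It is short, about 32 × 20 = 640 person-days, and subjects who miss the in-person baseline visit are withdrawn (Section 4.3.1).

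Third, the rate is unknown, and the artefact is small if subjects average three or more episodes per 180 days. That is correct.

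Some stronger readings are tempting but not supported:

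- A reader might infer that a formal before/after test of utilization is planned. Section 6.2.1 assigns tests to dichotomous and timed variables, with pairing in Stage 2, and names none for event counts.
- A reader might infer that the contrast will supply an effect size for the next trial. Section 1.1.3 speaks only of possible inclusion of measures.
- A reader might infer that the secondary utilization endpoint shares the look-back. Sections 1.2 and 4.3.3 do not include it.
- A reader might infer that Stroop, ANT and SF-8 carry the same artefact. They do not use the look-back; they share only the lack of a control.

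**Conclusion.** The point holds, at minor to moderate severity. Stage 2 cannot determine efficacy, and that limit covers every before/after comparison in Section 1.1.3.

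For HE utilization, the look-back is expected to inflate the pre-enrollment rate. With a constant rate and no effect, the false fall per day is 61% to 2% for L from 0.5 to 4, and 44%, 25% and 11% at L = 0.5, 1 and 2 with exponential variation between patients. The direction is certain only under a constant rate. If risk is raised after an episode, the size changes by an amount that the documents do not determine, and at very high recurrence the sign can reverse. On raw counts, the direction depends on L.

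The look-back comparison appears only in exploratory aim 5. The primary endpoints, retention and adherence, are unaffected.

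**What to change.** **Section 1.** Replace the clause on determining the efficacy of MTM with: describe changes during and after MTM.

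**Section 1.1.3, aim 5.**

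- Use the 90-day pre-enrollment counts as baseline description only.
- Report post-enrollment utilization as events per person-time, with 95% confidence intervals that allow for variation between patients. Do so separately for run-in (before meals start, about Day 32), the MTM period and the observation period.
- If a contrast with the look-back is still shown, express it per person-time. State that selection on a recent HE episode is expected to inflate the pre-enrollment rate, and do not use the contrast as an effect size for the future trial.
- Label any version that removes the qualifying episode as a sensitivity analysis, and say which episode was removed.

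**Cost.** This changes wording and reporting only; Table 2 already plans chart review of utilization. The downside is that Stage 2 can make no before/after efficacy statement on utilization, and that its rates will be imprecise. Twenty subjects followed for 172 days give 3,440 person-days. At L = 1 that is about 19 HE episodes, with an exact Poisson 95% interval of 0.60 to 1.55 per 180 days. Variation between patients would widen it, as would splitting by period: the 640 person-days of run-in would yield only about 640/180 = 3.6 episodes.
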